Moreover, increased V-ATPase activity determines an extrusion of H⁺ ions in the extracellular environment that can positively affect different pro-tumoral activities. In fact, a decrease of extracellular pH leads to activation of proteases able to destroy the extracellular matrix. Such activity enhances tumor spreading. Moreover, a low extracellular pH can reduce the efficacy of antineoplastic agents since a low pH might affect the structural integrity of drugs and their ability to pass through the plasmatic membrane. Finally, V-ATPase can act as an active pump able to excrete antineoplastic agents¹⁵.

For this reason, PPIs are considered new anti-cancer drugs able to increase tumoral cell death, reduce tumor invasion and increase chemotherapy efficacy¹⁴.

Moreover, GBMs with high V-ATPase expression has proved to be able to transmit highly malignant features through a network of MVs and to activate proliferation of GASC *in vitro* through the transmission of G1 subunit of V-ATPase^{9,27}.

In this view, our work is intended to study: 1) the effects of PPIs on CSC and GASCs cultures as in vitro add-on treatments; 2) the MVs load in terms of miRNAs and DNA (ssDNA, exoDNA²⁸) during the neuro-oncological follow-up in order to understand how it changes after surgery and adjuvant treatments; 3) the possible roles of V-ATPase as a clinical marker to be used to check tumor response to adjuvant treatments.

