2.4 Study Population

Planned number of subjects undergoing surgical removal of intra-axial brain tumor at the Neurosurgical Division of Ospedale San Gerardo: almost 45 per year. Thirty patients are expected to have a glioma of which 25 patients are expected to be diagnosed with a GBM and 5 with a LGG. We plan to enroll 25 patients/year.

STUDY NAME: Vacuolar ATPase and drug resistance of high grade gliomas: a study to investigate possible therapeutic roles for proton pump inhibitors. STUDY CODE: GLIODRUG-V	Ver. 1.0 07/06/2019
---	------------------------

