2.7 Experimental Design

Our study will use glioma tissues, after all sampling for diagnosis will be collected. Moreover, we will take blood samples from patients undergoing surgery for HGGs and during the oncological follow-up. Tumor samples will be harvested in order to obtain parallel tumor cultures to test *in vitro* tumor sensitivity to different chemotherapies, with and without inhibition of V-ATPase. Moreover, we will analyze the expression of V-ATPase (especially subunit V1G1) in vesicles released by cancer cells, in order to understand how V-ATPase can influence drug resistance and tumor progression. HGG-released vesicles will be also isolated in the circulation from patients' blood in order to analyze tumor responses to oncological treatments and the genetic and epigenetic status of the tumor, including amplification of oncogenes (i.e. *c-Myc*), and the content of specific coding and non-coding RNA, DNA and retrotransposon elements, through the use of next generation sequencing (NGS)²⁸.

Duration for enrollment: 24months;

Duration for follow-up analysis: 12 months for each patient.

Maximum length of the study: 36 months including patients' follow-up

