Anti-neoplastic agents taken into account for this study are: Temozolomide, Vincristine, Carboplatin, Etoposide, Irinotecan (CPT-11), Bevacizumab, BCNU, CCNU, Procarbazine, Irinotecan + Carboplatin, Procarbazine + Vincristine + CCNU (PCV). All these agents have been used for treatment of HGGs as first or second line therapy.

PPIs used for this study are: concanamycin, Bafilomycin-A1, Archazolide-A. All the procedures will be performed for research use at the Medical Genetics Laboratory ([name]), of School of Medicine and Surgery, University of Milano-Bicocca..

Part 3 – serial analysis of blood samples

During the first year of neuro-oncological follow-up, patients will undergo to collection of blood samples pre- and post-operatively, three months, six months, nine months and one year after surgery. Each sample will be processed in order to study the MVs content of subunits of V-ATPase (especially subunit V1G1) and the genetic and epigenetic content (DNA, mRNA and miRNA). The results will be matched with the brain MRIs performed as part of the neuro-oncological follow-up. The blood volume will be of about 5-10 mLs and it will be taken during the normal blood sampling performed during the neuro-oncological follow-up for checking chemotherapy toxicities. No adjunctive invasive procedures will be performed on patients.

During this part of the study, it will be possible to understand the relations between tumor volume and MVs concentrations in the bloodstream in order to understand the role of surgery on the existing vesicular network between the brain and the rest of the body. Moreover, it will be possible to study the effects of adjuvant treatments on the MVs contents during the time of response to treatment and at tumor recurrence. Finally, analysis of DNA, miRNA and mRNA contained in the MVs will allow us to explore the presence of new markers able to predict tumor recurrence and to understand *in vivo* any possible changes of the neoplastic cells during the treatment.

These results will be compared with the results obtained *in vitro* in order to understand if the experimental model can reflect the mechanisms active in the patient.

This part of the research project will allow us to transfer the project from the bench to the bedside and it will be the starting point for future projects.

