3.7 Neuro-Oncological Follow-up

All patients will undergo to a neuro-oncological follow-up. Each patient will be treated with a standard first line treatment according to the Stupp protocol with concomitant chemo-radiation therapy and subsequent adjuvant chemotherapy. Every 3 months, each patient will undergo a brain MRI.

During every neuro-oncological evaluation, each patient will have a blood sample taken in order to check the blood count. During this standard procedure, an additional sample of blood will be taken for this study in order to extract circulating exosomes and DNA.

Brain MRIs will be examined to calculate tumor volumes and residual tumor volumes and to diagnose tumor recurrence.

3.8 Statistical analysis.

Data will be expressed as median and interquartile range (IQR), number and relative percentage, or hazard ratio (HR) with related 95% confidence intervals (CI). Normal distribution of continuous variables will be assessed by Kolmogorov-Smirnov test. To compare baseline characteristics of the groups in the univariate analysis, continuous variables will be analysed using the Mann-Whitney test or ANOVA according to the type of distribution. Categorical variables will be analyzed by Fisher exact test or Chi-Square Test as

STUDY NAME: Vacuolar ATPase and drug resistance of high grade gliomas: a study to investigate possible therapeutic roles for proton pump inhibitors. STUDY CODE: GLIODRUG-V	Ver. 1.0 07/06/2019
---	------------------------

appropriate. A 1:1 propensity-score-analysis, with a caliper of 0.1SD, may be conducted for significant variables ($p < 0.05$) at univariate to reduce the retrospective bias of selection.

Multivariate analysis will be performed by logistic regression analysis or Cox regression as appropriate. DFS, OS and TSS will be evaluated by Kaplan-Meier method. Comparison between groups will be performed with the log-rank test. A Receiver Operating Characteristic (ROC) curve analysis will be employed as appropriate. The optimal cut-off value will be established based on the Youden index. All statistics will be 2-tailed and statistical significance will be accepted when $p < 0.05$.

3.9 Data management.

Data will be stored in an electronic database. Each investigator may have access to the whole dataset.

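### The Youden cut-off is chosen and judged in the same cohort of about 50 patients, so its accuracy is overstated, and testing the resulting groups at 0.05 would be too liberal

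*Protocol*

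**What the plan says.** All the analysis rules are in Protocol section 3.8. ROC analysis is to be used where suitable, and then: "The optimal cut-off value will be established based on the Youden index". On survival: "Comparison between groups will be performed with the log-rank test". On modelling: "Multivariate analysis will be performed by logistic regression analysis or Cox regression as appropriate". On significance: "All statistics will be 2-tailed and statistical significance will be accepted when" p is below 0.05.

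Section 3.8 does not name the marker or the outcome for the ROC curve, and it does not define the groups in the log-rank sentence. The aims supply the likely markers. Section 2.1 lists "the possible roles of V-ATPase as a clinical marker to be used to check tumor response to adjuvant treatments", and section 3.5.1 (Part 3) wants to "explore the presence of new markers able to predict tumor recurrence" from vesicle DNA, miRNA and mRNA.

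On size, section 2.4 says "We plan to enroll 25 patients/year", and section 2.7 gives 24 months of enrolment and "Duration for follow-up analysis: 12 months for each patient". Section 2.3 describes one prospective cohort. No second cohort, resampling correction or pre-set cut is mentioned.

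**The concern.** The Youden index is J = sensitivity + specificity - 1, and the optimal cut is the one with the largest J in the observed data. The maximum over many candidate cuts picks up chance as well as signal. Accuracy quoted at that cut, in the patients who chose it, will on average be better than it would be in new patients. In a cohort this small the gap is large.

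A second problem follows if the high and low groups at that cut are compared on the same outcome. The test then treats as given a grouping that was selected to make the outcomes differ, so its p-value is not valid at 0.05.

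Section 3.5.1 presents the blood-marker work as the basis for later projects. An inflated cut-off, or a marker that is significant only because its cut was tuned, would be carried into those projects.

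**Working it through.** The Protocol gives no expected AUC, J or power, so there is no figure of its own to reproduce.

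**Inputs from the Protocol**
- Sample size: 25 per year x 2 years = 50 at most, before exclusions and withdrawals (2.4, 2.7). n=25, one year's enrolment, is the lower case.
- Follow-up: 12 months each (2.7).
- Median overall survival: 14-16 months for glioblastoma (section 1); 15 used.

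**Assumptions**
- Median time to recurrence of 8 months. Section 2.1 says only that recurrence is generally expected within 12 months.
- Exponential times, censoring at 12 months, one normally distributed marker value per patient, cut chosen on 12-month event status.
- Share with the event by 12 months: 1 - 2^(-12/8) = 65%, and 1 - 2^(-12/15) = 43%.

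**Step 1: apparent J of a useless marker (true J = 0).** With direction fixed, the maximised J is a one-sided two-sample Kolmogorov-Smirnov statistic. With m events among N patients its large-sample mean is 0.627 x sqrt(N/(m(N-m))).
- N=50, m=25: 0.627 x sqrt(50/625) = 0.18; simulated 0.157.
- N=25, m=12: 0.627 x sqrt(25/156) = 0.25; simulated 0.217.

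The formula runs a little high in small samples, so the simulated values (20,000 replicates) are used. Over event shares of about 30-80%, mean apparent J is 0.22-0.27 at n=25 and 0.16-0.20 at n=50. If the direction is also chosen from the data, it is 0.31-0.39 and 0.23-0.29.

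**Step 2: false positives if the groups are tested.** Null marker, nominal two-sided 5%. Rejection rates are from 10,000 replicates per row, J from 3,000.

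| n / median (months) | Mean J, direction fixed | Log-rank, fixed | Log-rank, free | Fisher, fixed | Fisher, free | Log-rank, median split | Continuous Cox |
|---|---|---|---|---|---|---|---|
| 25 / 8 | 0.233 | 17.5% | 28.0% | 9.1% | 18.6% | 5.2% | 5.6% |
| 25 / 15 | 0.224 | 19.3% | 31.1% | 10.0% | 20.0% | 5.4% | 5.7% |
| 50 / 8 | 0.170 | 19.1% | 31.6% | 12.8% | 25.5% | 5.0% | 5.3% |
| 50 / 15 | 0.165 | 20.8% | 35.2% | 13.3% | 26.2% | 4.8% | 5.0% |

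A second simulation of the log-rank test (3,000 replicates) gave 17.5-20.5% (fixed), 27.2-34.6% (free) and 4.5-5.9% (median split). In the runs with fixed event counts, the lowest Fisher rate found was 6.5% (n=30, 15 events). The median split uses the same patients and the same test and stays near 5%, so the excess comes from letting the outcome choose the cut, not from the sample size.

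Relative to 5%: 9.1/5 = 1.8 and 35.2/5 = 7.0, so about two to seven times nominal across the table.

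**Step 3: a marker with real value.** With an assumed hazard ratio of 1.7 per SD and n=50, apparent J is 0.37-0.42, against 0.24-0.28 when the same cut is applied to new patients.

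**Step 4: does the remedy work?** Repeated 5-fold cross-validation that re-derives the cut in each fold brings the null-marker J to between -0.01 and 0.00. Bootstrap optimism correction still leaves 0.06-0.09. Power at n=50 and hazard ratio 1.7 per SD is 66-81% for continuous Cox and 45-62% for a median split.

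**The case against.** The strongest objection is that the Protocol never says the Youden groups are tested. In section 3.8 the word groups first appears with baseline characteristics and propensity matching. The log-rank sentence comes before the ROC sentences, and Fisher's test is introduced for categorical variables in the univariate comparison. The log-rank groups may be something else entirely. That stands, and it is why the p-value part is conditional. It does not touch the accuracy part, which follows from the cut-off rule alone.

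Section 3.8 also names no marker or outcome. That stands too; the link to V-ATPase and vesicle content comes from the stated aims.

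Internal validation is often left to a statistical analysis plan, which is not at hand. But the Protocol does more than stay silent: it prescribes a data-driven cut without qualification.

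The marker work is exploratory, the primary objective is in vitro, and no treatment decision hangs on the cut. This limits the consequence, but section 3.8 does not label the cut exploratory.

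The magnitudes depend on assumptions. The 8-month median and the hazard ratio of 1.7 are not in the Protocol. The 15-month median is for treated glioblastoma, while eligibility covers gliomas generally. The seven-fold figure is the worst cell; with direction fixed, the natural case for the V1G1 subunit, log-rank is about four times nominal. The direction of the bias does not depend on these choices.

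**Conclusion.** The concern holds. Followed as written, section 3.8 yields a cut-off whose apparent accuracy is too good. For a useless marker the average J is about 0.16-0.17 with 50 patients and 0.22-0.23 with 25, with direction fixed and 43-65% of patients having the event. It is higher if outcomes are more unbalanced or the direction is picked from the data. For a useful marker, apparent J exceeds its value in new patients by roughly 0.13-0.14 (range midpoints 0.395 and 0.26).

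Conditional on the Youden groups being tested in the same patients, the false-positive rate is above 5% in every setting examined: 17-21% (log-rank) or 9-13% (Fisher) with direction fixed, and 28-35% or 19-26% with direction free, as for newly sought RNA or DNA markers. These are rates per marker.

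This should be corrected before the marker analysis. It does not affect the in vitro primary objective.

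**What to change.** Amend section 3.8 as follows:

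1. Test V1G1 and the other vesicle markers as continuous variables, log-transformed if skewed, in the Cox or logistic models already planned.
2. Name the marker and outcome for each ROC curve, and summarise it by AUC with a 95% confidence interval.
3. Report the Youden cut as descriptive and exploratory only, with sensitivity and specificity from repeated 5-fold cross-validation that re-derives the cut in each fold.
4. Form Kaplan-Meier and log-rank groups at a cut fixed before outcomes are seen, such as the cohort median. Say what those groups are.

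If a test at the Youden cut is still wanted, use a permutation or maximally selected p-value that repeats the cut search.

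The cost is a few sentences and a few lines of code, with no new data. Cross-validated accuracy will be lower, and it is noisy at n=50. The continuous model assumes a roughly log-linear effect. Fewer results will be nominally significant. The median split loses power against the continuous model, so the continuous model should carry the inference and the split should serve for display.

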4 CRF

4.1 Rules for completing CRFs

The investigator staff must ensure that all information derived from source documentation is consistent with the source information. By uploading the complete dataset, the Investigator confirms that the information is complete and correct.

4.2 Corrections to CRFs

Corrections to the data on the CRFs can only be made by communicating to the Data Manager the alphanumeric code linked to the name of the patient and asking to modify the data.

5. Ethics

The register will be conducted in accordance with the Declaration of Helsinki and according to local and regional ethical standards.

5.1 Critical documents

Before the Investigator starts the study (i.e., obtains informed consent from the first subject), the following documents must be available:

- Regulatory approval and/or notification as required
- Signed and dated agreement on the final protocol
- Signed and dated agreement on any substantial amendment(s), if applicable
- Approval/favourable opinion from IEC clearly identifying the documents reviewed: the

protocol, any substantial amendments, subject information/informed consent form and any other written information to be provided to the subject, subject recruitment procedures.

6. Significance and Innovation

This work is meant to increase our knowledge on glioma progression and on drug resistance of high grade gliomas and the role played by V-ATPase. First, this study is meant to better investigate the role of V-ATPase on drug resistance and the possible roles that V-ATPase inhibitors could play as add-on treatments for HGGs. This would be one of the first dedicated study in literature and it could set the theoretical bases for an *in vivo* study.

Secondarily, this study is meant to investigate the molecular changes that tumors may develop through the analysis of MVs and circulating DNA during the normal neuro-oncological follow-up. The aim is to find molecular settings that might underpin the resistance to adjuvant treatments or that might be involved in developing drug resistance during the neuro-oncological follow-up and that could be related with development of tumor recurrence.

STUDY NAME: Vacuolar ATPase and drug resistance of high grade gliomas: a study to investigate possible therapeutic roles for proton pump inhibitors.	Ver. 1.0 07/06/2019
STUDY CODE: GLIODRUG-V	

This study might allow in future to understand new strategies to increase the efficacy of adjuvant treatments against HGGs. These treatments will aim to dismantle the tumoral cell metabolism blocking the mechanisms that regulate the intracellular pH.

7. Responsibilities

The Investigator is accountable for the conduct of the study. If any tasks are delegated, the Investigator should maintain a list of appropriately qualified persons to whom he/she has delegated specified significant study-related duties.

The medical care given to, and medical decisions made on behalf of, subjects should always be the responsibility of a qualified physician.

The Investigator will take all necessary technical and organizational safety measures to prevent accidental or wrongful destruction, loss or deterioration of data. The Investigator will prevent any unauthorized access to data or any other processing of data against applicable law.

8. Reports and publications

The information obtained during the conduct of this study is considered confidential and belongs to the investigator group for the purpose of scientific publications. No confidential information shall be disclosed to others. Such information shall not be used except in the performance of this study group.

All the investigators may decide after a consensus, to share the data with other groups or trials occasionally. In this case, the agreement of the whole study group is needed.

9. Retention of clinical documentation

Subject notes must be kept for the maximum period permitted by the hospital, institution or private practice.

The Investigator must agree to archive the documentation pertaining to the register in an archive after completion or discontinuation of the study if not otherwise notified.

Clinical study documentation must be retained until at least 2 years.

STUDY NAME: Vacuolar ATPase and drug resistance of high grade gliomas: a study to investigate possible therapeutic roles for proton pump inhibitors. STUDY CODE: GLIODRUG-V	Ver. 1.0 07/06/2019
---	------------------------

10. References

4. Martínez-García M, Álvarez-Linera J, Carrato C, et al. SEOM clinical guidelines for diagnosis and treatment of glioblastoma (2017). *Clinical and Translational Oncology*. 2018;20(1):22-28. doi:10.1007/s12094-017-1763-6
